11.2. Overview of Other Safety Analyses

Table 7 provides an overview of the planned analyses for laboratory data, immunogenicity, ECG and vital signs. Full details of the data displays to be presented are given in Appendix 8: List of Data Displays.

Table 7 Overview of Other Safety Analyses

Endpoint / Parameter/ Display Type	Absolute			Change from BL		
	Summary		Individual	Summary		Individual
	T	F	L	T	F	L
Haematology						
Haematology Changes from Baseline				Y		
Haematology Shifts from Baseline Relative to Normal Range				Y		
Haematology Shifts from Baseline Relative to PCI Range				Y		
Haematology Data for Subjects with Any Value of Potential Clinical Concern			Y			
Chemistry						
Chemistry Changes from Baseline				Y		
Chemistry Shifts from Baseline Relative to Normal Range				Y		
Chemistry Shifts from Baseline Relative to PCI Range				Y		
Chemistry Data for Subjects with Any Value of Potential Clinical Concern			Y			
ECG						
ECG Findings	Y					
Vital Signs						
Vital Signs Change from Baseline				Y		
Injection Pain Assessment						
Injection Pain VAS Scores	Y		Y			
Injection Pain Categorical Pain Assessment	Y		Y			

NOTES:

- T = Table, F = Figures, L = Listings, Y = Yes display generated. PCI = Potential Clinical Importance – see Section 14.6.
- Summary = Represents TFL related to any summaries (i.e. descriptive statistics) of the observed raw data.
- Individual = Represents FL related to any displays of individual subject observed raw data.

11.2.1. Injection Pain Assessment

Injection pain assessed immediately after the injection and at 1 and 24 hours post-injection, will be summarised by visit and time point. Summary statistics of the Visual Analogue Scale (VAS) score for injection pain will be presented. Categorical summaries of pain description (sharp/stinging, dull/aching, burning, other), pain relative to expectation (greater than expected, less than expected, as expected) and acceptability of pain will also be summarised. All injection pain data will be listed.

12. IMMUNOGENICITY ANALYSES

12.1. Overview of Immunogenicity Analyses

For the immunogenicity assessment, two types of anti-drug antibody (ADA) assays will be performed, a binding antibody assay and a neutralizing antibody assay.

For the binding assay, there will be a three tiered analysis: screening, confirmation and titration. The screening assay produces a result of positive or negative relative to a screening cut point. Positive samples continue with the confirmation assay, which also produces a result of positive or negative relative to a confirmation cut point. For positive confirmation samples, a titre value will also be obtained to quantify the degree of binding in a titration assay and the sample will be tested with the neutralizing assay, which also reports results as positive or negative.

The binding ADA results at Week 0 and Week 12/Early withdrawal will be summarised by visit. Summary statistics for the titre result at Week 12/Early Withdrawal will also be presented. Summaries will also be produced by visit and baseline mepolizumab use.

A summary of adverse events by Week 12/Early Withdrawal binding ADA result will be produced.

A summary of liquid treatment emergent positive confirmatory binding ADA assays in the subset of subjects who did not have a positive confirmatory binding ADA assay prior to the first dose of liquid study treatment at Week 0 will also be presented.

Neutralizing antibody assay results will be summarised by visit, and by visit and baseline mepolizumab use.

Immunogenicity data will be listed for subjects with at least one positive screening binding assay.

14.1. Appendix 1: Time & Events

14.1.1. Protocol Defined Time & Events

	Pre-screening Week - 6 to Week -5 ^a	Screening Week -4 to Week -1	Week 0 (Day 1)	Week 4 (±7 days)	Week 8 (±7 days)	Week 12 (±7 days) End of Study/ Early Withdrawal ^b
Procedures Visit number	V0	V1	V2	V3	V4	V5
Informed consent	X					
Demography/child bearing status assessment	X					
Medical history		X				
Asthma and Exacerbation history	X					
Asthma Therapy history	X					
Smoking history		X				
Parasitic screening ^c		X				
Prior needle use / self-administration assessment		X				
Inclusion/Exclusion criteria		X				
Training session			X ^d			
Safety syringe self-administration in clinic			X		X	
Safety syringe self-administration outside of clinic				X ^{e, f}		
Laboratory:						
Urine pregnancy test		X	X ^d	X ^d	X ^d	X
Hematology (including eosinophils) ^g / Clinical Chemistry		X	X ^d	X ^d	X ^d	X ^d
Urinalysis		X				
Immunogenicity			X ^d			X ^d
PK			X ^d	X ^d	X ^d	X ^d
Pharmacogenetics ^h			X			
Physical/Clinical:						
Vital signs ⁱ		X	X ^d	X ^d	X ^d	X
12-lead ECG		X				X
Physical examination		X				X

CONFIDENTIAL

205667

	Pre-screening Week - 6 to Week -5 ^a	Screening Week -4 to Week -1	Week 0 (Day 1)	Week 4 (±7 days)	Week 8 (±7 days)	Week 12 (±7 days) End of Study/ Early Withdrawal ^b
Procedures Visit number	V0	V1	V2	V3	V4	V5
Weight		X				
Concomitant Medication	X	X	X	X	X	X
Serious Adverse Events ^{j,k,l}	X	X	X	X	X	X
Adverse Events ^{j,k,l}			X	X	X	X
Dispense patient diary			X ^m	X	X	
Return/review patient diary				X	X	X ⁿ
Dispense safety syringe for self-administration outside of clinic				X		
Return/ inspect safety syringe following self-administration outside of clinic					X	X ^{n,o}
Subject completed pain assessment diary (0, 1- and 24hours post dose)			X	X ^f	X	
Safety syringe observer assessment checklist			X		X	
Subject/caregiver completed safety syringe checklist				X ^f		
Assessment of injection success			X		X ^p	
Device usability/functionality questionnaire						X
Exit Interview ^q						(X)

- a. Pre-screening Visit can occur on the same day as the Screening Visit but must be completed prior to initiating any Visit 1 procedures; The Pre-screening Visit can be conducted up to a maximum of 2 weeks prior to the Screening Visit.
- b. The Early Withdrawal Visit will occur 4 weeks (±7 days) after last dose of mepolizumab for any subject who withdraws prior to Week 12
- c. Parasitic screening is only required in countries with high-risk or for subjects who have visited high-risk countries in the past 6 months. Sites should use local laboratories.
- d. Perform prior to mepolizumab administration during the study and prior to restarting pre-study mepolizumab treatment on study completion/early withdrawal.
- e. Subjects will be instructed to contact clinical study staff at any time if they have concerns or questions regarding self-administration. They will have the option of returning to the clinical site for further training or assistance with self-administration. Requirement for additional training or assistance will be documented.
- f. Self-administration of mepolizumab using the safety syringe should occur within 24 hours following the clinic visit.
- g. Includes measurement of eosinophil levels for pharmacodynamic analysis at Visits 2, 3, 4 and 5
- h. Pharmacogenetic sample may be drawn any time after the respective informed consent form is signed and the subject is enrolled.
- i. Vital signs include temperature, sitting blood pressure, respiratory rate and pulse.

CONFIDENTIAL

205667

- j. Any SAEs assessed as related to study participation (e.g., study treatment, protocol-mandated procedures, invasive tests, or change in existing therapy) or related to a GSK concomitant medication, will be recorded from the time a subject consents to participate in the study up to and including any follow up contact. All other AEs/SAEs are recorded from the start of study treatment until the End of Study / Early Withdrawal visit.
- k. Injection site reactions (e.g., induration, erythema, edema, rash, pruritus, pain) are to be recorded on both AE and SAE CRF forms.
- l. Information on systemic reactions and events that meet the anaphylaxis criteria is collected on both AE and SAE CRF forms.
- m. Patient diary should be dispensed prior to administration of injection
- n. For any subject who withdraws prior to Week 12, patient diary and study drug for self-administration outside of clinic will be returned at the Early Withdrawal visit (if applicable).
- o. Assessment to be completed at the Early Withdrawal visit only if the dose of mepolizumab immediately prior to withdrawal was administered outside of the clinic.
- p. Includes both the injection outside the clinic from Week 4 and the injection in clinic at Week 8
- q. In a subset of subjects only. Completed over the telephone after the End of Study/Early Withdrawal Visit

14.2. Appendix 2: Treatment States and Phases

14.2.1. Treatment Phases

Assessments and events will be classified according to the time of occurrence relative to the first dose of study treatment.

14.2.1.1. Treatment Phases for Adverse Events

Treatment State	Definition
Pre-Treatment	
 AE start date < First dose of study treatment
On-Treatment	
 First dose of study treatment ≤ AE start date ≤ First dose of study treatment + 28 days Any adverse event with missing start date will be assumed to be “On-Treatment”. Any adverse event with partial start date will be assumed to be “On-Treatment” unless there is evidence to the contrary (e.g. month/year of onset is present and is earlier than the month/year of the first dose of study treatment).
Post-Treatment	
 AE start date > First dose of study treatment + 28 days

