4.2. Treatment Arms and Duration

This is a single arm study in which all subjects will receive mepolizumab 100 mg SC every 4 weeks, using the liquid drug product in safety syringe presentation, for 12 weeks. Each subject will participate in the study for up to 18 weeks (Visit 0 to the End of Study Visit (Visit 5) as described in [Table 1](#).

Table 1 Study Phases

Phase	Phase Title	Duration	Description
1	Pre-screening	0 to 2 weeks	At the Pre-screening Visit, details about the study and procedures will be explained through the informed consent process. The Pre-screening Visit (Visit 0) can occur on the same day as the Screening Visit (Visit 1) but must be completed prior to initiating any Visit 1 procedures.
2	Screening	1 to 4 weeks	Subjects will be assessed for eligibility at the Screening Visit (Visit 1). Blood draws will be taken for assessments of liver function and to determine blood eosinophil levels in subjects not previously using mepolizumab and who do not meet the historical blood eosinophil criterion.
3	Treatment	12 weeks	At Visit 2 (Week 0) those subjects who continue to meet the eligibility criteria and the continuation to treatment criteria (see Section 5.3) will receive mepolizumab 100 mg SC every 4 weeks for a total of 3 doses. The treatment period will conclude with subjects completing End of Study Visit (Visit 5) assessments approximately 4 weeks after the subject was administered their last dose of study treatment at Visit 4.

A subject who adheres to the study treatment and assessment schedule (as detailed in Time and Events Table, Section 7.1) will be considered to have completed the study if they complete all of the assessments at the End of Study visit (Visit 5). A subject who permanently discontinues study treatment early will be withdrawn from the study after completing the Early Withdrawal visit (see Time and Events Table, Section 7.1).

Subjects receiving mepolizumab prior to the study will be advised to continue with their pre-study mepolizumab treatment following completion of the assessments at the End of Study/Early Withdrawal visit. Subjects not receiving mepolizumab prior to the start of the study will have mepolizumab treatment stopped at the End of Study/Early Withdrawal visit and will receive appropriate care and treatment as determined by their treating physician.

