14.2.1.2. Treatment Phases for Exacerbations

Treatment State	Definition
Pre-Treatment	
 Exacerbation onset date < First dose of study treatment
On-Treatment	
 First dose of study treatment ≤ exacerbation onset date ≤ First dose of study treatment + 28 days Any exacerbation with missing onset date will be assumed to be “On-Treatment”. Any exacerbation with partial onset date will be assumed to be “On-Treatment” unless there is evidence to the contrary (e.g. month/year of onset is present and is earlier than the month/year of the first dose of study treatment).
Post-Treatment	
 Exacerbation onset date > First dose of study treatment + 28 days

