14.4.2. Study Population

Demographics
Age

 GSK standard IDSL algorithms will be used for calculating age where birth day and month will be imputed ‘30th June’. Birth date will be presented in listings as ‘YYYY’. Age will be calculated relative to the date of the screening visit (Visit 1).
Body Mass Index (BMI)

 Calculated as Weight (kg) / [Height (m)]²
Disease Duration

 Calculated in years as Number of Years + (Number of Months)/12
Extent of Exposure

 Number of months of exposure to liquid mepolizumab during this study will be calculated based on the formula: Duration of Exposure (Months) = (Date of Last Dose of Study Treatment – Date of First Dose of Study Treatment + 29) * 12/365.25

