14.8. Appendix 8: List of Data Displays

14.8.1. Study Population Tables

Study Population - Tables					
No.	Population	IDSL / TST ID / Example Shell	Title	Programming Notes	Deliverable [Priority]
6.1	ASE	TAB_POP1	Summary of Study Populations		SAC
6.2	ASE	ES6	Summary of Screen Failures	Include footnote "Note: Inclusion/exclusion criteria include protocol defined continuation criteria."	SAC
6.3	ASE	NS1	Summary of Number of Subjects by Country and Site	"Not Treated" column should be added to include subjects who did not receive treatment.	SAC
6.4	All Subjects	SD1	Summary of IP Discontinuation		SAC
6.5	All Subjects	ES1	Summary of Subject Disposition		SAC
6.6	All Subjects	DV1	Summary of Important Protocol Deviations		SAC
6.7	All Subjects	EX1	Summary of Exposure to Study Treatment (months)	Categories 1, 2, 3 months Summary statistics for duration of exposure (months)	SAC
6.8	All Subjects	TAB_EX1	Summary of Injection Site by Visit		SAC
6.9	All Subjects	DM1	Summary of Demographic Characteristics		SAC
6.10	All Subjects	DM5	Summary of Race and Racial Combinations		SAC
6.11	ASE	DM11	Summary of Age Ranges	"Not Treated" column should be added to include subjects who did not receive treatment.	SAC
6.12	All Subjects	TAB_POP2	Summary of Disease Duration		SAC
6.13	All Subjects	TAB_POP3	Summary of Prior Experience with Self-Injection of Medication		SAC
6.14	All Subjects	TAB_POP4	Summary of Baseline Mepolizumab Use		SAC
6.15	All Subjects	MH1	Summary of Past Medical Conditions		SAC
6.16	All Subjects	MH1	Summary of Current Medical Conditions		SAC
6.17	All Subjects	FH1	Summary of Family History of Cardiovascular Risk Factors		SAC

Study Population - Tables					
No.	Population	IDSL / TST ID / Example Shell	Title	Programming Notes	Deliverable [Priority]
6.18	All Subjects	SU1	Summary of Smoking History	Smoking status (current/former/never) only	SAC

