		Liquid Safety Syringe (N=XX)
1	All Events >= 1 event [1]	xx/xx (x%)
	1 event	xx (x%)
	2 events	xx (x%)
	3 events	xx (x%)
	>=4 events	xx (x%)
2	Serious Events >= 1 event [1]	xx/xx (x%)
3	Events considered related to investigational product >= 1 event [1]	xx/xx (x%)
4	Intensity [1]	
	Mild	xx/xx (x%)
	Moderate	xx/xx (x%)
	Severe	xx/xx (x%)
5	Outcome [1]	
	Recovered/Resolving	xx/xx (x%)
	Recovering/Resolving	xx/xx (x%)
	Not recovered/Not Resolved	xx/xx (x%)
	Recovered/Resolved with sequelae	xx/xx (x%)
	Fatal	xx/xx (x%)

[1] Information presented as number of events / number (%) subjects with at least one event. Subjects may be counted in more than one row.

[2] Cardiac History=Yes includes all subjects with any past medical condition under Cardiac Disorders.

[3] Unable to categorise time since last dose as event time not reported.

userid: /arenv/arprod/compound/study/final/drivers/drivename.sas DDMMYYYY HH:MM

Example TAB_S1 (Cont.)
 Protocol: MID205667
 Population: All Subjects (Safety)

Table X.X

Summary Profile of On-Treatment Adverse Events Defined by the Investigator as Allergic (Type I Hypersensitivity) Reactions

		Liquid Safety Syringe (N=XX)
6	Action Taken [1]	
	Study treatment withdrawn	xx/xx (x%)
	Dose reduced	xx/xx (x%)
	Dose increased	xx/xx (x%)
	Dose not changed	xx/xx (x%)
	Dose interrupted/delayed	xx/xx (x%)
	Not applicable	xx/xx (x%)
7	Cardiac History [1][2]	
	Yes	xx/xx (x%)
	No	xx/xx (x%)
8	Anaphylaxis Criteria Met	
	Anaphylactic Criterion 1	xx/xx (x%)
	Anaphylactic Criterion 2	xx/xx (x%)
	Anaphylactic Criterion 3	xx/xx (x%)
9	No. doses prior to event [1]	
	1	xx/xx (x%)
	2	xx/xx (x%)
	3	xx/xx (x%)
	etc.	
10	No. doses prior to first event	
	1	xx (x%)
	2	xx (x%)
	3	xx (x%)
	etc.	

[1] Information presented as number of events / number (%) subjects with at least one event. Subjects may be counted in more than one row.

[2] Cardiac History=Yes includes all subjects with any past medical condition under Cardiac Disorders.

[3] Unable to categorise time since last dose as event time not reported.

userid: /arenv/arprod/compound/study/final/drivers/drivername.sas DDMMYYYY HH:MM

Example TAB_S1 (Cont.)
 Protocol: MID205667
 Population: All Subjects (Safety)

Table X.X

Summary Profile of On-Treatment Adverse Events Defined by the Investigator as Allergic (Type I Hypersensitivity) Reactions

	Liquid Safety Syringe (N=XX)
11	Time since last dose to event onset [1]
	<=1 hr xx/xx (x%)
	1-<6 hrs xx/xx (x%)
	6-<24 hrs xx/xx (x%)
	>=24 hrs xx/xx (x%)

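### The on-treatment phase ends 28 days after the first dose, not the last, so the AESI and exacerbation summaries cover about one third of a three-dose, 12-week treatment period

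*SAP*

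**What the plan says.** SAP 14.2.1 opens its phase rules with: "Assessments and events will be classified according to the time of occurrence relative to the first dose of study treatment". For adverse events, on-treatment means "First dose of study treatment ≤ AE start date ≤ First dose of study treatment + 28 days", and post-treatment means "AE start date > First dose of study treatment + 28 days". SAP 14.2.1.2 repeats the construction for exacerbations: "First dose of study treatment ≤ exacerbation onset date ≤ First dose of study treatment + 28 days". Events with a missing date, or with a partial date and no evidence to the contrary, are assigned to the on-treatment phase.

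The design has repeated dosing. Under Protocol 4.2, subjects "will receive mepolizumab 100 mg SC every 4 weeks for a total of 3 doses", and the treatment phase lasts 12 weeks. Protocol 7.7.1.1 collects AEs from Visit 2 to the End of Study or Early Withdrawal visit.

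Elsewhere the SAP uses the last dose. The exposure calculation in 14.4.2 is built on "Date of Last Dose of Study Treatment – Date of First Dose of Study Treatment + 29", and Table 6.7 reports exposure as "Categories 1, 2, 3 months".

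**The concern.** A window anchored on the first dose suits a single-dose study. Here it labels subjects post-treatment while they are still being dosed. Dose 2, the unobserved injection outside the clinic, falls at or near the end of the window, and dose 3 falls well outside it.

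The label decides what is tabulated. By title, all 18 AESI tables (anaphylaxis, systemic reactions, local injection site reactions and the rest) and the sole exacerbation table are on-treatment only. Systemic reactions, injection site reactions and exacerbations are named safety endpoints in Protocol Section 3. SAP 2.2 defines the exacerbation endpoint as the number of subjects with at least one exacerbation, but its only summary would count roughly the first 4 weeks over the full denominator. Table 11.8 would set Week 12 antibody results against AEs from the first 28 days alone.

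**Working it through.** **Inputs.** Day 0 is the first dose.
- Doses every 4 weeks, three in total (Protocol 4.2): nominal days 0, 28 and 56.
- Visit 3 at Week 4 ±7 days and Visit 4 at Week 8 ±7 days (Protocol 7.1). Assumption: windows are counted from Visit 2, which gives days 21–35 and 49–63.
- Dose 2 up to 24 hours after Visit 3 (Protocol 6.8.2): days 21–36.
- On-treatment window (SAP 14.2.1.1 and 14.2.1.2): days 0–28.

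**The plan's own period.** Last dose plus one dosing interval is (56 + 28)/7 = 12.0 weeks, which matches the stated treatment period. The exposure formula gives (56 − 0 + 29) × 12/365.25 = 2.79 months, or 85 inclusive days. This also fits the 1, 2 and 3 month categories.

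**The window as written.** Days 0–28 are 29 inclusive days. 29/85 = 34% (28/84 = 33% as elapsed time). In months this is 29 × 12/365.25 = 0.95, against 2.79 of exposure.

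**Cover after dose 2.** Days inside the window from dose 2 on day d: max(0, 28 − d + 1).

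| Dose 2 on day | Days covered |
|---|---|
| 21 (earliest) | 8 |
| 28 | 1 |
| 29 or later | 0 |

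In the most favourable schedule (dose 2 on day 21, dose 3 on day 49), 8 of the 28 days between the two doses are covered, or 29%.

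**Cover after dose 3.** The earliest scheduled dose 3 is day 56 − 7 = 49, and 49 − 28 = 21 days after the window closes. Cover is 0 days on any schedule within the visit windows.

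**Tables affected (SAP 14.8.5 and 14.8.6, by title).**
- On-treatment: 5 AE (11.1, 11.3, 11.4, 11.5, 11.8) + 2 SAE (11.15, 11.16) + 18 AESI (11.20–11.37) = 25.
- Post-treatment: 2 (11.2, 11.17).
- Pre-treatment: 1 (11.18).
- No phase stated: 7 (11.6, 11.7, 11.9, 11.10, 11.13, 11.14, 11.19).
- Total: 25 + 2 + 1 + 7 = 35.
- Exacerbations: 1 of 1 on-treatment only (10.1).

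**Illustration only.** The documents give no expected exacerbation incidence. Assume a 12-week incidence P and a constant hazard. The share seen in the window is then 1 − (1 − P)^(28/84), or with exponent 29/85.
- P = 10%: 3.45% to 3.53%. In 55 subjects, 5.5 become about 1.9.
- P = 20%: 7.2% to 7.3%. In 55 subjects, 11 become about 4.0.

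**The case against.** The strongest reply is that nothing is lost and little depends on it. The study is descriptive with no hypothesis test, and the injection-success endpoints do not use these phases. Later AEs and SAEs go to Tables 11.2 and 11.17. Drug-related events, discontinuations, fatal SAEs and events on the day of dosing have no phase limit in their titles. Every AESI type and every exacerbation is listed. All of this is true, and it limits the consequence. It does not repair the AESI and exacerbation incidences: Table 11.2 is by system organ class and preferred term, so a later AESI is identified as one only in a listing.

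Four narrower points also stand:
- Only fully dated events are certain to be excluded. Events with missing or partial dates can enter the on-treatment tables even if they followed dose 3.
- The exact figures for the earliest doses 2 and 3 depend on counting visit windows from Visit 2.
- The AESI profile shell has rows for two and three prior doses, which the written rule leaves almost or wholly empty of fully dated events. The shell is partly generic, so this is weak evidence of intent.
- Protocol 9.4.2 sets no phase cut-off and Protocol 9.3 defers detail to the analysis plan. The absence of a declared change in SAP 2.1 therefore adds little. The exposure formula and the dosing schedule carry the argument.

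**Conclusion.** The concern holds. The first-dose anchor stands in four bounds and the lead-in, and nothing elsewhere overrides it, so programming that follows the SAP would implement it. For a subject dosed on schedule, the on-treatment phase holds 29 of 85 planned days: at most 1 day from dose 2 onward and none after dose 3. If fully dated AESIs or exacerbations start after day 28, the 18 AESI tables and Table 10.1 understate their incidence, and the other seven on-treatment AE and SAE tables omit such events too. How large the understatement would be cannot be derived from the documents; the 10% and 20% examples rest on assumed incidences and a constant hazard. The day counts need only the dosing schedule and, for the extremes, the visit-window assumption. Subjects who take only dose 1 are unaffected. The definition should be corrected before the tables are produced.

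**What to change.** In SAP 14.2.1.1 and 14.2.1.2, replace first dose + 28 days with last dose + 28 days in the two on-treatment upper bounds and the two post-treatment lower bounds. Amend the 14.2.1 lead-in to refer to the first and last doses of study treatment. On schedule the window then ends on day 84 and covers all 85 days, in line with the exposure formula in 14.4.2.

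The cost is five wording changes and one derivation, with no extra data or tables. Reported AESI and exacerbation incidences will be higher if later events occur.

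A small remainder should be acknowledged. Because the final visit may be as late as day 91, 7 collected days can fall after last dose + 28 when dose 3 is on day 56 (91 − 84), and 14 when it is on day 49 (91 − 77). AESIs or exacerbations starting in those days would still be identified as such only in the listings.
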